Official Title: The Effect of a Gait Modification Training Program on Impact Loading and Running-related Injuries

NCT Number: NCT03302975

The Effect of a Gait Modification Training Program on Impact Loading and Running-related Injuries

Objectives

The purpose of this study is to determine whether a gait modification training program can result in a reduction in impact loading and the incidence of running-related injuries (RRI) among recreational distance runners. Knee angle at initial contact (IC) has been identified in a previous study by the principal investigator (pre-submission stage) as both increasing the average vertical loading rate (AVLR) and the incidence of RRI in the female recreational running population. This variable will be modified to determine the effect on impact loading (AVLR) and incidence of RRI using a repeated measures design.

Background

Numerous studies have shown that individuals can be trained to modify aspects of walking and running[1-18]. Moreover, gait retraining has been shown to be effective in treating overuse injuries in runners[4,7,8,18]. However, since it is unclear what variables independently contribute to the recovery from these injuries and whether these variables can be manipulated prospectively to reduce the risk of injury, optimal prevention and treatment of RRI remains unknown. These studies all included some form of feedback to the subjects, which helped them modify their technique. The feedback methods included verbal instructions and real-time visual[1,3,6,7,9,12,17,18] or auditory information[4,5,8,11,15,16]. Other studies used verbal instructions and videotape reviews[13,14] or an extensive training program[8,19]. Many of these studies have used

overlapping instructions and feedback which make it difficult to infer which factors had a causative effect on changing gait mechanics, muscle activation patterns, and ground reaction forces. Others have used feedback that is difficult to reproduce outside of a lab or clinic environment. Simple cues that produce a specific and intended kinematic or spatiotemporal modification are necessary. Furthermore, these cues need to be consistent and reproducible in multiple training environments in order to be retained as part of the motor program.

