Arendse et al[19] reported that 7.5 hours of training over 5 consecutive days was required to learn FF landing, while Dallam et al[20] reported a 1-hour session for 12 weeks was necessary. Diebal et al showed FF landing could be trained in 6 weeks, with training sessions 3 times per week for 45 minutes[8]. An 8-session faded-feedback approach was used by Barrios et al to retrain walkers. This design produced changes in lower extremity biomechanical variables immediately post-intervention as well as at 1-month follow-up [1]. Subjects who receive intermittent feedback have been shown to perform better in the long-term than subjects who receive continuous immediate feedback[21,22]. Removing the feedback is beneficial to motor skill learning because the subjects must rely on internal cues for performing correct motor patterns[23].

Some researchers have suggested that further studies should investigate the effect of gait retraining on injury prevention in runners[8,19]. Changing a runner's gait to reduce the risk of a certain injury, however, may have unintended consequences such as increasing the chance of another kind of injury if other kinematic or spatiotemporal variables are adversely impacted[2,19]. Knowledge of the independent contributions of identified kinematic and spatiotemporal risk factors to impact loading and injury

incidence will allow for targeted modification of these variables so that the risk of negative consequences is limited.

Hypotheses

It is hypothesized that after a 15-week training program, a change in knee flexion at IC will be significant ($p < 0.05$) and will result in decreased impact loading (AVLR) and incidence of RRI.

Outcome Measures

Primary outcome measures:

- 1) Kinetic outcomes: Average vertical loading rate (Body weights [BW] per second) and vertical impact peak (BWs).
- 2) Incidence of RRI (calculated as the number of new injuries reported per 100 runners at risk).

Secondary outcome measures:

Secondary outcome measures will be kinematic and/or spatiotemporal correlates of impact loading and incidence of RRI as guided by the literature and determined in previous studies.

- 1) Knee flexion angle at IC
- 2) Peak knee flexion angle
- 3) Angle of the shank at IC

Other outcome measures:

Other outcome measures will be collected to describe and assess the success of the gait modification intervention. These measures include:

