- 1) Participant compliance: Participant compliance with the gait modification intervention will be measured by the number of training sessions attended at Fortius (to a maximum of 8, converted to a percentage) and the number of home training sessions completed (to a maximum of 22, converted to a percentage). Participants will record their home training sessions in their weekly online questionnaire.
- 2) Adverse events: Adverse events experienced due to the intervention (i.e. increased pain or a new injury) will be recorded in the weekly online questionnaires.
- 3) Fidelity of training sessions: Assessed by calculating the difference (error, in degrees) between the intended target angle and the actual angle produced during the 10 consecutive stance phases at each of the four time points during each training session (first min, 33%, 66%, and last min) and averaged within the session.
- 4) Perceived difficulty in achieving targeted modification: Assessed at each training session using an 11-point numerical rating scale (NRS) (0 = “no difficulty”, 10 = “unable to perform”).
- 5) Pain: Assessed at each training session using an 11-point NRS (0 = “no pain”, 10 = “worst pain imaginable”).
- 6) Rating of Perceived Exertion (RPE): Assessed at each training session using the 15-point Borg RPE scale.

- 7) Anthropometric and functional measurements: These will include BMI, navicular height, hip internal/external rotation range of motion, Q-angle, and weight-bearing ankle dorsiflexion and knee valgus angle.

Methods

The proposed study is a repeated measures design. A sample size calculation for comparing injury incidence is based on our current injury rate (27.9%) in our previous studies. We calculate that we will require a sample size of 30 to achieve a minimum power of 80% ($\alpha = 0.05$). Thirty uninjured female recreational runners will be recruited through advertisements in Vancouver-area running clinics. Participants must be female between the ages of 18 and 60; have been running for at least three months prior to study commencement; and have experience with running on a treadmill. Participants must not have run more than two half marathons previously. Participants will be excluded if they have experienced a lower extremity injury in the prior three months; have undergone hip, knee, or ankle joint surgery; or currently have pain in their lower back or lower extremities while running.

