Eligible participants will first be screened for the biomechanical trait in question (less than 10° of knee flexion at IC). A historical control group from a previous study will be used as a comparison group and a sample that meets the same screening criteria will be matched for age and BMI.

Demographics and a detailed training and injury history will be taken for each subject, which will include information on running experience, previous best times at 5km, 10km, half marathon and marathon distances (if available), and overall number and

type of general musculoskeletal and/or running injuries. Anthropometric and functional measurements (including height, mass, foot length, navicular height, hip internal/external rotation range of motion, Q-angle, and weight-bearing ankle dorsiflexion) will be collected prior to treadmill testing for descriptive purposes and for use as covariates. Participants will wear their regular running shoes.

[figure not shown]

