Pain, RPE, and perceived difficulty in achieving the targeted modification will be measured in all training sessions using an 11-point NRS (pain and perceived difficulty) and the Borg RPE scale. Adverse events (increased pain or a new injury) and participant compliance with the gait intervention will be assessed in the weekly online questionnaire.

All participants will return to the Fortius Biomechanics Lab at the conclusion of the 15-week half-marathon clinic for retesting. A one-month post-test will also be performed to assess for retention. During both sessions (follow-up and retention), the participants will be asked to run naturally and then with the modified pattern. The natural pattern will be collected to determine whether it has changed since baseline.

The verbal instruction during each training session will be given by the principal investigator (a sport physiotherapist with clinical experience in gait retraining). The therapist will not be involved in data collection, but will process the data. To ensure blinding, data will be collected by an independent lab assistant and coded to blind for participant number for later processing and analysis by the principal investigator. This process will ensure that the principal investigator is unaware of which participant they are analyzing until the conclusion of the study.

Demographic, anthropometric, and functional variables will be analyzed for differences between the intervention group and a historical control group from our previous studies at baseline using 2-tailed t-tests for normally distributed continuous variables. Injury incidence (number of new injuries reported per 100 runners at risk) will be compared between groups using paired t-tests. Differences in outcomes pertaining to the feasibility of the intervention (perceived difficulty, exertion, fidelity, compliance) will

be assessed in the intervention group between session 1 and 8 using paired t-tests. The biomechanical and clinical outcomes from the follow-up and one-month post-intervention modified patterns will be compared to the baseline values using ANOVAs for repeated measures. Planned pairwise comparisons between the visits will be conducted. Differences will be considered statistically significant at $p < 0.05$. All statistical analyses will be performed using SPSS version 22.0 (SPSS Inc., Chicago, IL).

References

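### The paired t-test named for injury incidence does not fit an outcome defined as one rate per group, and the plan fixes neither the pairs nor the per-runner score it would need

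*Combined protocol and SAP*

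**What the plan says.** Outcome Measures lists injury as the second primary outcome: "Incidence of RRI (calculated as the number of new injuries reported per 100 runners at risk"). That is one figure for each group.

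The Methods describe the design in these words: "The proposed study is a repeated measures design". The injury comparator, however, is a historical control group from a previous study, of which "a sample that meets the same screening criteria will be matched for age and BMI". No matching ratio, caliper, pair list or number of controls is given.

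The last paragraph of the Methods names the test: "Injury incidence (number of new injuries reported per 100 runners at risk) will be compared between groups using paired t-tests". The same paragraph does three other things that bear on the point:

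- It compares the same two groups at baseline with two-tailed t-tests that are not called paired.
- It uses paired t-tests for session 1 against session 8 within the intervention group, where true pairs exist.
- It says the biomechanical outcomes "will be compared to the baseline values using ANOVAs for repeated measures".

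The sample-size sentence in the Methods is "based on our current injury rate (27.9%) in our previous studies". A percentage used in this way reads more like a proportion of women injured than a count of injuries.

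**The concern.** A paired t-test needs one score per runner and a list saying which runner goes with which control. The plan states neither. The outcome as defined gives a single rate in each group, and the women in the two groups are not the same women.

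This is the only test named for injury incidence and the only between-group efficacy test named in the plan. The analyst would have to settle the pairs and the score later. The control women's injury results come from a previous study, so those choices could be made with the results in view, and the plan contains no rule against it. At stake is whether a borderline injury result is declared significant at 0.05.

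**Working it through.** **The plan's own figure.** The only related number is N = 30 for at least 80% power at a 27.9% injury rate. It cannot be reproduced, because no expected intervention rate is given. For 30 v 30, two-sided, a two-proportion calculation reaches 80% only if the intervention rate is about 2.5% or lower. That is a separate matter; what follows does not depend on it.

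**Step 1: the test on the outcome as defined.** One rate per group gives one difference. The paired t-test has (number of pairs − 1) = 1 − 1 = 0 degrees of freedom, so it cannot be computed.

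**Step 2: what makes it computable.** It needs 1:1 pairs and a score per runner. Assume 30 controls (the number is not given) and a yes/no score. Let A controls and B recruits be injured, with k pairs in which both are injured. Then i = A − k pairs have only the control injured and j = B − k have only the recruit injured. With n = 30:

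- mean difference d = (i − j)/n
- variance v = [(i + j) − n·d²]/(n − 1)
- t = d/√(v/n) on 29 degrees of freedom

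**Step 3: a borderline example.** Take 8/30 v 2/30 injured; 27.9% of 30 is 8.4, so 8 is close to the cited rate. Here d = 6/30 = 0.2 and n·d² = 1.2 whatever the pairing. Under random pairing, the probability of k is hypergeometric with C(30,2) = 435 in the denominator.

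| Both-injured pairs k | i, j | v | t | p | Probability of k |
|---|---|---|---|---|---|
| 0 | 8, 2 | (10 − 1.2)/29 = 0.303 | 0.2/0.1006 = 1.99 | 0.056 | 231/435 = 0.531 |
| 1 | 7, 1 | (8 − 1.2)/29 = 0.234 | 0.2/0.0884 = 2.26 | 0.031 | 176/435 = 0.405 |
| 2 | 6, 0 | (6 − 1.2)/29 = 0.166 | 0.2/0.0743 = 2.69 | 0.012 | 28/435 = 0.064 |

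The injury totals are identical in all three rows. About 47% of pairings (0.405 + 0.064) are significant. On the same totals Fisher's exact test gives p = 0.080 and exact McNemar gives 0.109, 0.070 or 0.031.

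**Step 4: other totals.** Share of random pairings with p < 0.05:

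| Injured, control v recruits | Share |
|---|---|
| 8 v 1 | 100% |
| 9 v 2 | 100% |
| 10 v 3 | 72% |
| 9 v 3 | 21% |
| 8 v 3 | 1.4% |

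**Step 5: averaged over trials.** Weight each pair of totals by its binomial probability. Call the verdict pairing-dependent when 5% to 95% of pairings are significant (a conventional cut-off, not from the plan).

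| Setting | Equal rate | Halved | A third |
|---|---|---|---|
| Controls 27.9%, random pairing | 4.8% | 14% | 17% |
| Controls 27.9%, pairs within strata of 5 per group | 5.3% | 14% | 18% |
| Controls 27.9%, strata of 3 | 4.5% | 12% | 15% |
| Controls 27.9%, strata of 2 | 3.7% | 9.1% | 11% |
| Controls 40%, random pairing | 6.0% | 17% | 17% |

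The strata rows mimic matching on age and BMI of increasing tightness (simulated, equal risk across strata). The 40% row is included because the 27.9% comes from previous studies in general. The controls would be women selected for a trait that the Objectives describe "as both increasing the average vertical loading rate (AVLR) and the incidence of RRI in the female recreational running population", so their rate may differ.

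**Step 6: the score.** With the pairs held fixed, scoring the same simulated data as a count and as yes/no gives opposite verdicts in 2.8%, 6.1% and 6.2% of trials (Poisson counts; any-injury risk 27.9% v the same, halved and a third). This is a smaller effect than the pairing.

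**Step 7: type I error.** With equal rates of 27.9% and pairing blind to outcome, the paired t-test rejects in 4.3% of trials and Fisher in 2.6%.

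**The case against.** The strongest defence is that matching for age and BMI, followed by the word paired, most naturally means individual 1:1 matching that was poorly written down. Likewise, injuries per 100 runners is 100 times the mean count per runner, so the written definition points to a count. Both readings are fair, and it would be wrong to say that pairs could not exist. But neither is stated. A matched sample can equally mean groups balanced on age and BMI, and the same paragraph compares these groups at baseline without pairing.

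It can also be said that on these figures most trials give the same verdict whichever pairing is used, and that close matching leaves fewer admissible pairings. That stands, and it limits the size of the point.

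Three stronger readings are tempting, and the documents do not support them:

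- **That the test is too liberal, or that a t-test is unsuited to these data.** With blind pairing it rejects at about 4.3% under the null, and it has more power than Fisher. No invalidity at 30 pairs is shown.
- **That the repeated-measures design offers no earlier injury value at all.** The exclusion reads: "Participants will be excluded if they have experienced a lower extremity injury in the prior three months". It covers only that site and window, and the Methods also collect an injury history with the number and type of past injuries. Whether those could serve is beside the point, because the plan states a between-group comparison.
- **That the kinetic primary outcomes share the problem.** They fall under the repeated-measures ANOVA and are not affected.

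**Conclusion.** The concern holds as one of a mis-specified and undetermined test, not of a falsely liberal one. The named test cannot be computed on the stated outcome. After pairs and a score are supplied, the choice of pairs can move a borderline result across 0.05, as 8/30 v 2/30 shows, while clearer totals are unaffected. The verdict depends on the pairing in roughly 5% of trials with no effect and in 14% to 17% if the injury rate is halved or cut to a third, and in fewer if matching is tight.

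These figures assume 30 controls, a yes/no score, controls at 27.9%, independent risks within pairs and random pairing; none of these is fixed by the plan. The statement on type I error holds only if the pairs are formed without sight of injury outcomes. That the historical controls are different women is inferred from their coming from a previous study. The point should be fixed before analysis, but it does not by itself invalidate the trial.

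**What to change.** 1. State the per-runner outcome: the number of new injuries, as the definition is now worded, or at least one new injury (yes/no), as the 27.9% suggests. The choice is the sponsor's. Yes/no alters the primary-outcome definition and should be labelled as a change.
2. State the number of controls and whether matching is individual 1:1.
3. Unless it is 1:1, replace the paired t-test with an independent-groups method: Fisher's exact or another two-proportion test for yes/no, or a Poisson or negative binomial rate comparison for counts.
4. If it is 1:1, fix the pair list from age, BMI and the screening trait without access to injury data. Then use a matched method: exact McNemar or conditional logistic regression for yes/no, or a paired comparison of counts such as a permutation test.
5. Report the risk or rate difference with a 95% confidence interval.

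The cost is a few sentences of analysis text and no new data. The downside is some loss of power if Fisher is used. At 30 per group, Fisher against the paired t-test has 17% v 23% power for 27.9% v 14% injured, and 44% v 55% for 27.9% v 7%.

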Participants will follow a 15-week half-marathon training program, wearing their regular running shoes throughout the study. During the training program, participants will attend the Fortius Biomechanics Lab on Weeks 1, 2, 4, 6, 8, 10, 12, and 14 (eight sessions in total) for a 15-30 minute gait modification training session following a faded-feedback design (figure 1)[1]. The aim of these sessions will be to modify the angle of knee flexion at IC so that it is greater than 10 degrees. Gait modification will be facilitated through the use of real-time biofeedback of performance[1,24,25] at each training session. The co-investigator, a sport physiotherapist, will also provide standardized verbal instructions to change the desired biomechanical outcome (e.g. “Land with a more bent knee”). For the first four sessions, participants will receive feedback for 100% of the session. By the eighth session, feedback will be provided for just 10% of the session (minutes 1, 15, and 30). All participants will have a total of 60 running sessions (four times per week for 15 weeks). During the weeks in which a lab-based gait modification session is scheduled, participants will have one lab-based biofeedback session and three “regularly scheduled” run sessions in which they will be instructed to focus on the same cues given in the lab during their runs. During the weeks in which no lab-based feedback session is scheduled,

participants will only have the four “regularly scheduled” run sessions in which they will be instructed to focus on the same cues given in the lab during their runs. This will ensure that they do not have any more run sessions than the historical control group.

Figure 1. Faded-feedback design depicting time spent running on the treadmill during each session and time with visual real-time biofeedback for each session. For the first four sessions, participants will receive feedback for 100% of the session. By the eighth session, feedback will be provided for just 10% of the session.

Kinetic, kinematic, and spatiotemporal data will be collected during each session to ensure that the goal of the intervention is being achieved. This will be assessed by calculating the difference (error, in degrees) between the intended target angle and the actual angle produced during the 10 consecutive stance phases at each of four time points during each training session (first min, 33%, 66%, and last min) and averaged within the

session.

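### Feasibility is tested only as session 1 against session 8 in runners who have both, so selective absence at week 14 could bias the change in either direction, and compliance cannot be paired at all.

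*Combined protocol and SAP*

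**What the plan says.** The statistical analysis paragraph of Methods has one sentence on feasibility. It begins "Differences in outcomes pertaining to the feasibility of the intervention (perceived difficulty, exertion, fidelity, compliance) will" and continues "be assessed in the intervention group between session 1 and 8 using paired t-tests". No analysis of sessions 2 to 7 is described, and the document has no missing-data rule, dropout allowance or definition of the analysis set.

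The measurements are much fuller than the test. Methods states that "Pain, RPE, and perceived difficulty in achieving the targeted modification will be measured in all training sessions". For fidelity, "Kinetic, kinematic, and spatiotemporal data will be collected during each session to ensure that the goal of the intervention is being achieved", with the angle error taken at four time points and averaged within each session. There are eight lab sessions, the first in week 1 and the last in week 14.

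Two other statements bear on the comparison. On feedback, "For the first four sessions, participants will receive feedback for 100% of the session", and by session 8 it covers only 10%. Item 1 of Other outcome measures says that compliance is "measured by the number of training sessions attended at Fortius (to a maximum of 8, converted to a percentage"), with home sessions counted in the same way to a maximum of 22.

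**The concern.** A paired t-test needs both members of each pair. A runner who attends seven sessions and misses the eighth contributes nothing, and with no missing-data rule that exclusion happens by default. Finding the new gait hard, having pain or picking up an injury are all plausible reasons not to attend in week 14, and they are close to what the feasibility outcomes measure. If absence and outcome are related, the runners left in the test are a selected group. The recorded sessions that could correct for this are left out of the analysis. At stake is whether the trial can say fairly that the modification became easier, less tiring or more accurate with training.

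**Working it through.** **Inputs from the documents.** 30 runners; 8 lab sessions; paired comparison of sessions 1 and 8; significance at p < 0.05; feedback 100% in sessions 1 to 4 and 10% at session 8. The plan gives no figure for the feasibility test, so there is none to reproduce: the sample size of 30 was derived for injury incidence.

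**Data used.** 30 × 8 = 240 possible session records, of which 30 × 2 = 60 enter the test (25%). That share is not an error in itself. With complete data, a mixed model with session as a categorical effect gives the same session 8 minus session 1 estimate as the paired mean difference. The other sessions matter when some runners lack session 8.

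**Direction of bias (all inputs assumed, none from the documents).** Difficulty at session j is 5 + u + (-0.25 + s)(j - 1) + e, with SDs 1.5 for the runner's level u, 0.25 for her slope s and 1.2 for the residual e. The true change is 7 × (-0.25) = -1.75 points; negative means easier. Runners with the highest leaving score lack session 8, where the score is a standardised driver plus independent standard normal noise. The driver's correlation with the score is then 1/√2 = 0.707. At 20% loss, those remaining have a mean driver of -0.707 × φ(0.842)/0.80 = -0.707 × 0.350 = -0.2475 SD. The bias in the paired change is:

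| What drives stopping | Bias at 20% loss | Simulated bias, 10% to 40% loss |
|---|---|---|
| Chance | 0 | 0.00 |
| Stable personal level | 0 (u cancels in the difference) | 0.00 |
| Observed session 1 difficulty | (-1.44/1.921) × (-0.2475) = +0.19 | +0.10 to +0.35 |
| Runner's own worsening slope | 7 × 0.25 × (-0.2475) = -0.43 | -0.24 to -0.80 |

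Here 1.44 = 1.2² and 1.921 = √(1.5² + 1.2²). A positive bias understates improvement and a negative one overstates it. The completers' session 8 mean, as distinct from the change, is better than the all-runner mean by about 0.2 to 0.8 points under each of the three non-random mechanisms.

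**Full-selection upper bound.** Suppose there is no true change, change is normal, and exactly the k runners with the worst change are missing. With c = Φ⁻¹(1 - k/30) and r = φ(c)/Φ(c), the mean of the rest is -r, the variance is 1 - cr - r², and t = -r√(30 - k)/SD.

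- k = 3: mean -0.195, SD 0.844, t = -1.20 (critical value 2.06)
- k = 5: mean -0.300, SD 0.787, t = -1.90 (critical value 2.06)
- k = 8: mean -0.448, SD 0.721, t = -2.91 (critical value 2.08)

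Only the last is significant. If leaving has correlation 0.5 with change, the means halve, the variances become 1 - 0.25(1 - SD²), and t falls to 0.53, 0.79 and 1.12 in absolute size. None is significant.

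**What a longitudinal model recovers.** These are simulations with no true change.

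- With the SDs above and dropout driven by recorded worsening (22% lost), the paired change was -0.47 points; a random intercept and slope model gave -0.03. With dropout driven by the latest recorded level (25% lost), the results were -0.27 and 0.00. A random intercept alone left -0.19 to -0.20.
- A separate check with 16% to 19% dropout gave paired biases of -0.38 (worsening), -0.13 (latest level) and +0.15 (session 1 level). The random intercept and slope model cut all three to about 0; a random intercept alone left up to -0.15. When dropout followed an unobserved slope, neither model removed the bias fully.

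**Compliance.** Sessions attended out of 8 and home sessions out of 22 are totals over the programme. Each runner has one value of each, so there is no pair to test.

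**The case against.** The strongest reply is that nothing in the documents shows that anyone will miss session 8. With full attendance there is no selection. Even with losses, the paired test removes the leaver's session 1 value too, so the bias in the change can be zero. This stands, and it limits the point to a risk of unknown size.

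A reader might infer that difficulty and fidelity will look better than they are. The documents do not support that. The direction depends on why runners stop, and the fall in feedback from 100% to 10% could make session 8 look worse whatever the attendance. A reader might also take the 27.9% injury rate as a forecast that about 8 of 30 runners (0.279 × 30 = 8.4) will be lost. It is an injury rate from previous studies, used for the sample size. Nothing says that an injured runner misses week 14 or has the worst change.

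It is also fair to say that stopping would be visible. Attendance is itself an outcome, adverse events are recorded weekly, and session data are collected to check that the target is being met. So sessions 2 to 7 are not without purpose; they are only absent from the planned test.

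Finally, the mixed model is not a strictly weaker assumption. The paired change stays unbiased when stopping depends on an unobserved stable level, which is not missing at random. What survives is that the stated test discards recorded information that can correct several plausible forms of selective loss.

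**Conclusion.** The point holds as a minor one. The feasibility test uses two of eight measured sessions and only runners with both, so selective absence at session 8 may bias the estimated change either way. The size cannot be fixed from the documents. The range of -0.80 to +0.35 points rests on assumed variances, 10% to 40% loss and the dropout mechanisms shown. The 0.19, 0.30 and 0.45 SD figures are ceilings under complete selection for 3, 5 and 8 absent runners, not expectations. Separately, and without any assumption, compliance as defined cannot be analysed by this test. Severity is minor because all four measures are listed as other outcomes.

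**What to change.** For difficulty, exertion and fidelity, replace the paired t-test with a linear mixed model on all eight sessions. Use session as a categorical fixed effect and a random intercept and slope per runner, and include every runner with at least one session. Estimate the session 8 minus session 1 contrast from that model. An unstructured covariance is an alternative, but it has 8 × 9/2 = 36 parameters for 30 runners, so the random intercept and slope is the safer default. A random intercept alone is not enough.

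Report how many runners reached session 8, the reasons for missed sessions, and the last observed values of those who did not reach it. State that the contrast combines learning with the withdrawal of feedback; sessions 1 to 4, all at 100% feedback, help to separate the two. Remove compliance from this test and summarise it descriptively.

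The cost is a few lines of analysis text and one standard model in the named software; the outcome data are already planned. The downside is the assumption that sessions are missing at random given those recorded. If stopping depends on unrecorded worsening, bias is reduced but not removed, and the report should say so.
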